4.4.2 Informed Consent

Prior to conducting any research procedures, the study investigator or designee must obtain consent from the patient or the patient's legally authorized representative. The signed consent form must be maintained with the patient's research chart and a copy must be provided to the patient or patient's legally authorized representative. See additional guidelines on informed consent in Section 9.1.

4.4.3 Physical Examination

4.4.3.1 Full Physical Exam

The Investigator or qualified designee will perform a complete physical exam during the Screening period. Clinically significant abnormal findings should be recorded as medical history. The time points for full physical exams are described in Section 5. After the first dose of trial treatment, new

Proprietary Information of MD Anderson

clinically significant abnormal findings should be recorded as AEs.

4.4.3.2 Directed Physical Exam

For cycles that do not require a full physical exam as defined in Section 5, the Investigator or qualified designee will perform a directed physical exam as clinically indicated prior to the administration of the trial treatment. New clinically significant abnormal findings should be recorded as AEs.

4.4.4 Eastern Cooperative Oncology Group (ECOG) Performance Scale

The investigator or qualified designee will assess ECOG status (see Appendix 4) at screening, additional time points for assessment of ECOG must be performed as per Section 5).

4.4.5 Vital Signs

Vital signs include temperature, pulse, respiratory rate, weight and blood pressure. The Investigator or qualified designee will take vital signs at screening, prior to the administration of each dose of trial treatment and during the follow-up period as specified in the Trial Flow Chart (Section 5). Height will be measured at Screening.

4.4.6 Response Assessment

MRI of the brain will be the primary radiological method of disease assessment using RECIST 1.1 and the RANO-BM criteria (See Appendix 1). Quantitative imaging changes on multiparametric MRI will be captured to determine early biomarkers of immune response. Standard of care brain MRI with intravenous gadolinium contrast and contrast enhanced CT chest/abdomen/pelvis or PET-CT, as clinically indicated, will be used to assess both intracranial and extracranial disease at Screening and every 6 weeks after the start of treatment up to cycle 9. Imaging may occur up to 72 hours prior to scheduled cycle. Screening MRI and CT assessments must occur within 28 days prior to day 1.

If an MRI, CT chest/abdomen/pelvis or PET-CT is not already performed as standard of care per Schedule of Assessments in Section 5, the investigator may choose to perform either or both procedures for assessing the progress of the patient.

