2 OBJECTIVES

2.1 PRIMARY OBJECTIVE

To assess clinical benefit rate (CBR), defined as CR + PR + SD > 6 months, in the brain in subjects with MBM per modified RECIST 1.1 criteria who are treatment naïve to anti-PD-1 agents in the metastatic setting (prior adjuvant anti-PD1 allowed. See inclusion and exclusion criteria).

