2.2 SECONDARY OBJECTIVES

1. To assess CBR in the brain in subjects with MBM per modified RECIST 1.1 in patients who previously progressed on PD-1 inhibitors.
2. To assess OS and PFS.
3. To evaluate the brain-specific safety and tolerability of the combination regimen in subjects with or without SRT received prior to study entry, or on study.
4. To evaluate cytokine levels and changes in the T-cell population in the cerebrospinal fluid (CSF) and blood in patients treated with combination low dose ipilimumab and pembrolizumab.
5. To assess changes in relative apparent diffusion coefficient as measured by MRI as an early predictor of response.
6. To assess changes in circulating cfDNA as determinants of response and/or markers of early progression.
7. To evaluate molecular and immunological changes in extracranial lesions.

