Subjects will undergo first CNS imaging evaluation at week 6 (\pm 3 days). Subsequently, subjects will be evaluated every 6 weeks (42 days \pm 3 days), independently of any treatment delays, with radiographic imaging to assess response to treatment, until week 30/Cycle 10. Subjects will then undergo imaging evaluation every 12 weeks (84 \pm 7 days). RECIST 1.1 will be used as the primary response rate efficacy endpoint. RECIST 1.1 will be adapted as described in Section 4. to adjust for the tumor response patterns seen with pembrolizumab treatment (e.g., tumor flare), and this adapted/modified RECIST 1.1 will be used by the sites for treatment decisions. The primary response rate efficacy endpoint will be based on independent central review using RECIST 1.1 [1]. Modified RECIST 1.1 will also be used by the local site to determine eligibility and make treatment decisions. MRI of the brain will be the primary radiological method of disease assessment using the RANO-BM criteria.

Subjects may submit an optional tumor tissue sample, if feasible, for biomarker analyses and PDL1 expression evaluation. Subjects with an inadequate archival sample may obtain a new biopsy and subjects with an inadequate newly obtained biopsy may undergo re-biopsy at the discretion of the investigator.

AEs will be monitored throughout the trial and graded in severity according to the guidelines outlined in the National Cancer Institute (NCI) Common Terminology Criteria for AEs (CTCAE) Version 4.03.

Treatment will continue as outlined in Table 1 until documented disease progression, unacceptable AEs, intercurrent illness that prevents further administration of treatment, investigator's decision to withdraw the subject, subject withdraws consent, pregnancy of the subject, noncompliance with trial treatment or procedure requirements, completion of 24 months of treatment with pembrolizumab, or administrative reasons.

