4.4.12.1.2 Blood

Blood will be collected for circulating chemokines, cell free DNA, PBMCs and T cell populations. Research blood will be drawn at each restaging imaging, and up to 40cc of blood will be drawn.

Proprietary Information of MD Anderson

This will be collected every 6 weeks beginning with Cycle 1 (pre-treatment) until Cycle 8.

- Functionality of circulating T cells and other immune markers in peripheral blood may be assessed utilizing 34 parameter mass cytometry (CyTOF) and/or flow cytometry. Cytokine analysis may also be performed on serum obtained from the same time points.
- Analysis of blood, availability permitting, may include also include molecular evaluations, to include circulating DNA and exosomal analyses.

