6.2.2 Secondary Endpoints

OS will be defined as the time from the start of first treatment to death for any cause. Patients who are still alive at the end of the study will be censored. PFS will be defined as the time from start of first treatment to disease progression or death for any cause. Patients who are still alive at the end of the study who had not progressed will be censored. OS and PFS will be assessed using the Kaplan-Meier method.

Cytokine levels and changes in the T-cell population in the CSF and blood will be summarized using means, standard deviations, medians, minimums, and maximums. Within group changes will be evaluated using either paired t-test or Wilcoxon signed rank test, depending on the data distribution.

Differences in the change in relative apparent diffusion coefficient and circulating cfDNA by CBR (yes vs. no) will be evaluated by either two sample t-test or Wilcoxon rank-sum test, depending on the data distribution.

Lastly, safety will be assessed by adverse events and serious adverse events as well as by vital signs and laboratory assessments for all patients. Categorical measures will be summarized using frequencies and percentages while continuous variables will be summarized using means, standard deviations, medians, minimums, and maximums.

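### The ADC and cfDNA comparison by final CBR has no fixed measurement time and can overlap with the week-6 scan that sets CBR for some patients, so a positive result would not by itself show early prediction

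*Combined protocol and SAP*

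**What the plan says.** Two secondary objectives in Section 2.2 concern the markers. Objective 5 reads "To assess changes in relative apparent diffusion coefficient as measured by MRI as an early predictor of response". Objective 6 reads "To assess changes in circulating cfDNA as determinants of response and/or markers of early progression".

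The only analysis given for either is in Section 6.2.2: "Differences in the change in relative apparent diffusion coefficient and circulating cfDNA by CBR (yes vs. no) will be evaluated", by two-sample t-test or Wilcoxon rank-sum test. That section names no time point for the change, no landmark, no analysis set and no significance level for this comparison.

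The timing comes from elsewhere in the protocol:

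- **MRI.** Section 3: "Subjects will undergo first CNS imaging evaluation at week 6". Section 4.4.6 places the quantitative MRI work inside response assessment: "Quantitative imaging changes on multiparametric MRI will be captured to determine early biomarkers of immune response". The schedule in Section 5 shows no earlier research MRI.
- **Blood.** Section 4.4.12.1.2: "Research blood will be drawn at each restaging imaging", every 6 weeks from a pre-treatment sample at Cycle 1 up to Cycle 8. The first on-treatment sample is therefore also at week 6.
- **Outcome.** Section 2.1: CBR is "defined as CR + PR + SD > 6 months, in the brain". The duration is attached to SD only, and Appendix 2 states no confirmation step for intracranial CR or PR.

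**The concern.** A predictor has to be read before the outcome is known. Here the earliest on-treatment marker value is taken at the same visit as the first response scan. A patient with lasting brain PD on that scan ends as CBR no. Under Section 2.1 with Appendix 2, a patient with CR or PR on it counts as CBR yes. For these patients the marker and the outcome come from the same day, yet Section 6.2.2 sets no restriction that would keep them out of the comparison.

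Because the time of the change is left open, the choice of scan or sample could also be made after the data are seen. Patients who stay on study will have later values that early progressors lack.

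What is at stake is interpretation. A marker that only mirrors current lesion size could be reported as meeting objective 5.

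**Working it through.** **1. The plan's own figures.** Section 6 gives no power or error rate for the marker analysis. The figures borrowed from Section 6.1 reproduce. With n = 25, 16% against 35% and one-sided 0.10, power is Φ[(0.19 − 1.282·√(0.16·0.84/25)) / √(0.35·0.65/25)] = 0.843, against the stated 84%. For Cohort B, 1 − 0.8⁵ = 0.672, against the stated 0.67.

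**2. Share of patients with progression by week 6.** The documents do not give this. As an assumption, take a constant progression hazard; 6 months is about 26.1 weeks and 6 weeks about 1.38 months.

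- If 35% are progression-free at 6 months (anticipated CBR used as a rough stand-in): 1 − 0.35^(6/26.1) = 0.21
- If 16% are (historical rate): 1 − 0.16^(6/26.1) = 0.34
- Using the 2.86-month median time to progression cited in Section 1.1.2.1 (a different setting): 1 − 0.5^(1.38/2.86) = 0.28

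That is about 5 to 9 of 25 patients. Early responders are probably few: the brain-metastasis trial cited in Section 1.2 had a median time to response of 2.8 months (range 1–11), so most responses would come after week 6.

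**3. How often would a non-predictive marker look positive?** Simulation with n = 25, CBR 35% and two-sided 0.05 (assumed, since the plan gives none):

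- The week-6 size change is standard normal and is cut into response (share r), SD and PD (share d).
- The marker is −ρ × size change plus independent noise, so it reflects size on the same day.
- Responders are CBR yes and PD patients CBR no. SD patients become CBR yes with probability (0.35 − r)/(1 − r − d), independent of the marker. For r = 5% and d = 20% this is 0.30/0.75 = 0.40.

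Proportion of trials with a significant all-patient t-test (ranges are repeat runs of the same model):

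| Response / PD at week 6 | ρ = 0.4 | ρ = 0.6 | ρ = 0.8 | Undecided of 25 |
|---|---|---|---|---|
| 0% / 28% | 10% | 15–16% | 26% | 18 |
| 5% / 20% | 10% | 18% | 29% | 19 |
| 5% / 28% | 13% | 24–26% | 41% | 17 |
| 10% / 30% | 16–17% | 32–34% | 55–58% | 15 |
| 15% / 40% | 23% | 47–50% | 78–79% | 11 |

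In patients still undecided at week 6 the proportion is about 5% in every row.

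A second model shifts the marker by 0.5, 1.0 or 1.5 SD between adjacent week-6 status groups. At 5% response and 20% PD it gives 7%, 14% and 24%; at 10% and 30% it gives 13%, 32% and 54%. With nobody decided at week 6 it gives 5%. Wilcoxon results are similar.

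**4. What a landmark costs.** The undecided set is 25 × (1 − r − d): 25 × 0.75 ≈ 19 in the mildest setting with responders, 25 × 0.45 ≈ 11 in the heaviest. Power follows from the noncentral t with parameter δ/√(1/n₁ + 1/n₀). For 5 against 6 patients and δ = 1 SD the parameter is 1/√(1/5 + 1/6) = 1.65, giving power of about 0.31; for δ = 0.5 SD power is about 0.11.

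**The case against.** The strongest reply is that the planned test is not wrong as a test. It asks whether the change differs by CBR, and in the simulated populations it does differ, because size drives both. The percentages above are then power to detect a real association, not a type I error rate. This is right. A reader might infer that the Section 6.2.2 test has an inflated error rate; the documents do not support that. The fault lies in reading the association as early prediction.

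Second, week-6 status can be provisional. Section 4.2.4 allows treatment through suspected pseudoprogression with a re-check about four weeks later. Appendix 1 recommends confirming progression three months later during the first six months, and says new lesions alone do not define it in that period. Its brain-metastasis table also requires CR and PR to last at least 4 weeks. This reduces the overlap but does not remove it: lasting PD remains decided, and Appendix 1 back-dates confirmed progression to the first scan that showed it.

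Third, a reader might infer that the week-6 scan settles CBR for most patients and that a spurious finding is more likely than not. The documents give no week-6 shares. The settings that produce rates of 50–80% assume more early response or progression, with a strong correlation, than the cited time to response and the hazard calculation suggest.

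Fourth, objective 6 includes markers of early progression, for which a same-day association is partly what is sought. Dropping the all-patient comparison would remove the very patients who progress early. This stands, and the fix keeps that comparison.

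Fifth, use of later scans is a possibility left open by the missing time point, not something the plan states.

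**Conclusion.** The point holds in a limited form. Section 6.2.2 leaves the time of the marker change open, and the first on-treatment ADC and cfDNA values come from the restaging that can already set CBR for some patients. A positive all-patient comparison would show an association that includes concurrent tumour status. By itself it would not support the claim in objective 5 of ADC change "as measured by MRI as an early predictor of response".

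On size: about 20–35% of patients may have progressed by week 6 under a constant hazard, plus a few early responders. With 5% response, 20–28% PD and correlations of 0.4–0.8, a marker with no information about later outcome gives a significant all-patient test in roughly 10–40% of trials, against about 5% in undecided patients. The week-6 shares, the correlations and the two-sided 0.05 level are all assumptions; the direction of the effect does not depend on their exact values.

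Severity is minor. These are secondary correlative analyses with no decision rule attached, and the primary CBR estimate is untouched.

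**What to change.** In Section 6.2.2:

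1. Define the marker change, for all patients, as baseline to the week-6 restaging.
2. Keep the all-patient comparison by CBR, but describe it as an association that includes concurrent tumour status. For cfDNA it remains relevant to early progression under objective 6.
3. For ADC (objective 5), and as supportive for cfDNA, add a week-6 landmark analysis in patients whose brain CBR is still undetermined after that scan. Report the difference in week-6 change by subsequent CBR as an estimate with a confidence interval, and base any claim of early prediction on it. State which response criteria decide who is undetermined, and how provisional week-6 calls are handled, using only what is known at the landmark.

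The cost is SAP wording and one extra analysis of data already collected, with no new scans, samples or patients. The drawback is precision: the landmark set is about 11–19 of 25 patients, fewer for cfDNA because research samples need optional consent (Section 4.4.12.1). Power is low, so a null landmark result should not be read as evidence that the marker has no value.

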4.4.7 Archival Tumor Tissue Sample

Archival tumor tissue samples obtained outside of this study for other purposes will be collected, if available, from all patients. All samples must be representative formalin-fixed paraffin-embedded (FFPE) tumor specimens in paraffin blocks (preferred) or at least 4 unstained slides, with an associated pathology report, for local testing of tumor PD-L1 expression.

4.4.8 Biopsy

Patients with biopsiable extracranial disease may have tissue collected pretreatment and at Cycle 2 (3 weeks after the start of treatment). Optional Biopsy may be collected at Cycle 5, if accessible, but is not required. If standard of care biopsies are required, additional, optional tissue may be acquired as part of this protocol. Acceptable samples include core-needle biopsies for deep tumor tissue (minimum of three cores) or excisional, incisional, or punch biopsies for cutaneous, subcutaneous, or mucosal lesions.

Acceptable samples include core needle biopsies for deep tumor tissue or lymph nodes or excisional, incisional, punch, or forceps biopsies for cutaneous, subcutaneous, or mucosal lesions.

Proprietary Information of MD Anderson

For core-needle biopsy specimens, at least three cores should be submitted for evaluation.

4.4.9 Laboratory Assessments

All labs will be processed locally at MDACC.

Hematology	Chemistry	Urinalysis	Other
Hematocrit	Albumin	Blood	Serum β -human chorionic gonadotropin† (β -hCG)†
Hemoglobin	Alkaline phosphatase	Glucose	
Platelet count	Alanine aminotransferase (ALT)	Protein	PT/INR
WBC (total and differential)	Aspartate aminotransferase (AST)	Specific gravity	aPTT
	Chloride	Urine pregnancy test †	Thyroid stimulating hormone (TSH)
Red Blood Cell Count	Lactate dehydrogenase (LDH)	Microscopic exam (If abnormal)	Total triiodothyronine (T3)
Absolute Neutrophil Count	Carbon Dioxide ‡	results are noted	Free thyroxine (T4)
Absolute Lymphocyte Count	(CO_2 or bicarbonate)		Blood for correlative studies
	Uric Acid		
	Calcium		
	Creatinine		
	Glucose		
	Magnesium		
	Phosphorus		
	Potassium		
	Sodium		
	Blood Urea Nitrogen		
	Total Bilirubin		
	Direct Bilirubin (If total bilirubin is elevated above the upper limit of normal)		
	Total protein		

† Perform on women of childbearing potential only. If urine pregnancy results cannot be confirmed as negative, a serum pregnancy test will be required.

‡ If considered standard of care in your region.

Proprietary Information of MD Anderson

4.4.10 Electrocardiogram

A standard 12-lead ECG will be performed using local standard procedures at Screening. Clinically significant abnormal findings should be recorded as medical history. Additional time points for standard 12-lead ECGs must be performed as per Section 5. Clinically significant abnormal findings seen on the follow-up ECGs should be recorded as adverse events.

4.4.11 Neurological Function Testing

Neurologic functioning will be evaluated using NANO. This objective and quantifiable assessment will evaluate nine major domains for subjects with brain tumors. The domains include: gait, strength, ataxia, sensation, visual field, facial strength, language, level of consciousness, behavior and overall. Each domain is rated on a scale of 0 to 3 where 0 represents normal and 3 represents the worst severity. A given domain should be scored non-evaluable if it cannot be accurately assessed due to preexisting conditions, co-morbid events and/or concurrent medications. The evaluation is based on direct observation/testing performed during routine office visits. The NANO scale will be completed by the investigator or designated study physician prior to dosing Day 1 Week 1 (baseline) and then at the time points indicated in on the schedule of events.

4.4.12 Research Sample Collection

4.4.12.1 Tumor Tissue Collection, Correlative Blood, and CSF Sampling

Correlative studies may be collected as specified in the study calendar, processed and/or stored for analysis with optional subject consent. All tissue and resulting data will be de-identified and may be shared between MD Anderson and the study supporter (Merck). All samples and data will be tracked utilizing a unique research tracking number that will not be related to any patient identifying information. The sample collections will be reported in the database and a source document will be printed for monitoring purposes. All samples will be stored at MD Anderson Melcore.

4.4.12.1.1 Tissue

Patients with biopsable extracranial disease for which tissue is collected (up to four cores) in accordance with the study schedule will be prioritized as follows:

- 25% (or one core) FFPE for histology and IHC studies
- 75% (or 3 cores) snap frozen in cryovials

Analysis of tissue, availability and quality permitting, may include the following studies:

- Immune monitoring and characterization of immune infiltrate in response to the drug combination using immunohistochemistry (IHC), characterization of PD-L1 expression, CD4, CD8 T cell infiltration.
- Molecular analyses on tissue samples and T cell infiltrates may include RNA based expression profiling (such as Nanostring via targeted panel or RNAseq) to evaluate immune gene expression signatures and the impact of the combination on treatment samples and correlating with clinical response data.

4.4.12.1.2 Blood

Blood will be collected for circulating chemokines, cell free DNA, PBMCs and T cell populations. Research blood will be drawn at each restaging imaging, and up to 40cc of blood will be drawn.

Proprietary Information of MD Anderson

This will be collected every 6 weeks beginning with Cycle 1 (pre-treatment) until Cycle 8.

- Functionality of circulating T cells and other immune markers in peripheral blood may be assessed utilizing 34 parameter mass cytometry (CyTOF) and/or flow cytometry. Cytokine analysis may also be performed on serum obtained from the same time points.
- Analysis of blood, availability permitting, may include also include molecular evaluations, to include circulating DNA and exosomal analyses.

4.4.12.1.3 Cerebrospinal Fluid (CSF)

CSF will be obtained from up to 5 patients for optional testing at baseline prior to the start of protocol treatment and again at the time of the first restaging scans.

Cytokine and circulating T-cell population in the CSF and PK/PD of ipilimumab and pembrolizumab in the CSF will be tested. Up to 20cc of CSF will be drawn via lumbar puncture in these patients.

4.4.13 Tumor Imaging and Assessment of Disease

All subjects will undergo CT scanning and volumetric MRI of the brain at the time points specified in the Schedule of Events in Section 5. CT and MRI scans will be assessed locally per the modified RECIST 1.1 criteria. Up to 5 systemic and 5 brain lesions will be followed for efficacy per the criteria.

